#### 9.2.3 Partial Implant

**Partial Implant** - refers to a subject who 1) has been enrolled in the MODULAR ATP Clinical Study, 2) has had either the S-ICD System introduced into their subcutaneous space or the EMPOWER MPS introduced into their vasculature, 3) is successfully implanted with either the S-ICD System or EMPOWER PG device, **but not both**, AND 4) is unable to or for whom there is no intention to implant the full mCRM Coordinated System.

Subjects classified as a Partial Implant that are implanted with an EMPOWER PG must be followed according to this protocol, with all relevant EMPOWER PG device data and
testing collected. Time 0 for the purpose of determining timing of follow ups for these subjects is the day it is determined the S-ICD will not be implanted.

Note that subjects implanted with an S-ICD System (prior to upgrading with clinical firmware in the MODULAR ATP Clinical Study) who are not implanted with an EMPOWER PG may be withdrawn from the MODULAR ATP Clinical Study after satisfying the follow-up of at least 30 days from S-ICD device implant.

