#### 9.2.2 Attempt

Attempt - refers to a subject who 1) has been enrolled in the MODULAR ATP Clinical Study, 2) has had anesthesia administered in preparation for the surgical implant procedure of an EMPOWER PG and/or S-ICD, but 3) is not successfully implanted with the EMPOWER PG and/or S-ICD.

Attempt subjects must be followed at least 30 days (either in-clinic or phone contact) post-attempted EMPOWER PG and/or S-ICD device implant to assure there are no associated adverse events or to assure the resolution of any adverse events associated with the attempted S-ICD and/or EMPOWER PG device implants. Attempt subjects will be included in the data analysis for the implant success rate. Attempt subjects must be withdrawn from the study after satisfying the follow-up of at least 30 days from attempted device implant.

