## 9.5 Withdrawal

All subjects enrolled in the clinical study (including those withdrawn) shall be accounted for and documented. If a subject withdraws from the clinical study, the reason(s) shall be

Reasons for withdrawal include, but are not limited to:

- Subject who does not receive either device for the purpose of supporting the study (EMPOWER PG or S-ICD). This includes subjects classified as "Intent", and those classified as "Attempt", according to the definitions in **Section 9.2**.
- Subject found to be ineligible to participate in the study prior to implant of the S-ICD and/ or EMPOWER PG (refer to **Section 9.2** for further information on follow up requirements)
- Physician discretion
- Subject choice to withdraw consent
- Explant of the investigational device(s) (EMPOWER PG and/ or S-ICD converted with clinical firmware) \*; subjects should be followed at least 30 days (either in-clinic or phone contact) post-explant of the mCRM Coordinated System to assure there are no associated adverse events or to assure the resolution of any adverse events associated with the explanted mCRM Coordinated System.
  - **\*Note**: this provision includes explant of the EMPOWER PG in all subjects, and the S-ICD in the case where the device has had clinical firmware uploaded.
- Lost to follow-up
- Death

While study withdrawal is discouraged, subjects may withdraw from the MODULAR ATP Clinical Study at any time, with or without reason, and without prejudice to further treatment. In cases of study withdrawal where the EMPOWER PG remains actively implanted, the subject should be informed that he/she will need to continue to have the EMPOWER PG evaluated per BSC's recommended follow-up (1, 3, 6 months and every 6 months) at a MODULAR ATP Clinical Study site where there is access to the investigational software (Model 3870) to interrogate the EMPOWER PG.

All applicable case report forms up to the point of subject withdrawal and an End of Study Form must be completed in eDC.

Additional study data may no longer be collected after the point at which a subject has been withdrawn from the study or withdraws his/her consent, for whatever reason. All open adverse events should be closed or documented as chronic. Data collected up to the point of subject withdrawal may be used.

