## Table 10-4: EMPOWER MPS Implant Source Documentation

## 10.3.1.10 Unsuccessful EMPOWER PG Implant

Subjects who are not successfully implanted with the EMPOWER PG (i.e., classified as "Attempt" subjects, as defined in **Section 9.2**) are to be withdrawn from the study after a minimum of 30 days from the implant procedure, including a required follow up either by phone or an in-clinic visit as included in **Section 9.2**. Attempted EMPOWER PG devices used in the implant procedure, but not implanted, must be reported on the appropriate *Device Tracking* Form in the database and returned to BSC.

Subjects who are not implanted with the EMPOWER PG, but who are implanted with an S-ICD System as part of the MODULAR ATP Clinical Study, are classified as "Partial Implant" subjects. Refer to **Section 9.2** for more information and follow-up requirements.

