### 11.1.1.3 Statistical Methods

Endpoint analysis will be performed on data from subjects that have undergone any portion of the EMPOWER PG implant procedure, including subjects that do not have the EMPOWER PG successfully implanted. The major EMPOWER MPS System and Procedure-related CFR from the date of the EMPOWER PG implant procedure through 6 months (180 days) post-implant will be calculated using Kaplan-Meier methodology.

The interim analysis will be conducted once 134 subjects have undergone the EMPOWER PG implant procedure and have been followed for 6 months (180 days). Using the allocated alpha level of 1.2% for the interim analysis, the 98.8% one-sided lower pointwise confidence limit of the Major CFR will be calculated via log-log methodology and compared to the performance goal of 86%. If the lower confidence limit exceeds 86%, the null hypothesis will be rejected.

If the interim analysis does not result in the rejection of the null hypothesis, the final analysis will be conducted once 223 subjects have undergone the EMPOWER PG implant procedure and have been followed for 6 months (180 days). Using the allocated alpha level of 1.9% for the final analysis, the 98.1% one-sided lower pointwise confidence limit of the Major CFR will be calculated via log-log methodology and compared to the performance goal of 86%. If the lower confidence limit exceeds 86%, the null hypothesis will be rejected.

The Kaplan-Meier methodology was chosen for this endpoint to utilize all available data for each subject. To assess the robustness of this analysis method and the potential impact missing data could have had on the analysis results, a tipping point analysis will be conducted that will include subjects that have undergone any portion of the EMPOWER PG implant procedure, including subjects that do not have the EMPOWER PG successfully implanted. The tipping point analysis will assign each subject with missing data as either having or not having a Major EMPOWER MPS System- and Procedurerelated complication. All possible combinations of these subjects' data will be evaluated along with the actual observed data to find the point, if any, at which the endpoint is failed.

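### A subject with an S-ICD and a failed EMPOWER attempt fits two classes with different 30-day clocks, and the 9.2.3 clock can expire less than 30 days after the attempt

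*Protocol*

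**What the plan says.** Four parts of the protocol bear on a subject who has an S-ICD and in whom the EMPOWER PG could not be implanted.

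- **9.2.2 Attempt.** The class covers a subject who had anesthesia for an implant but "is not successfully implanted with the EMPOWER PG and/or S-ICD". The follow-up rule is mandatory: "Attempt subjects must be followed at least 30 days (either in-clinic or phone contact) post-attempted EMPOWER PG and/or S-ICD device implant".
- **9.2.3 Partial Implant.** The class covers a subject successfully implanted with one device but not both. If the device is the S-ICD, the subject "may be withdrawn from the MODULAR ATP Clinical Study after satisfying the follow-up of at least 30 days from S-ICD device implant". The section sets no minimum time after a failed EMPOWER procedure.
- **10.3.1.10 Unsuccessful EMPOWER PG Implant.** The first paragraph treats subjects without a successful EMPOWER implant as Attempt; they "are to be withdrawn from the study after a minimum of 30 days from the implant procedure", with a phone or clinic contact required. The second paragraph says that subjects without an EMPOWER PG "but who are implanted with an S-ICD System as part of the MODULAR ATP Clinical Study, are classified as" Partial Implant, and refers back to 9.2 for follow-up.
- **9.5 Withdrawal.** The list of reasons places Attempt subjects among those who received neither device for the study. It also states: "Additional study data may no longer be collected after the point at which a subject has been withdrawn".

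On the analysis side, 11.1.1.3 runs Safety Endpoint 1 from the EMPOWER procedure date to 180 days in everyone who had any part of that procedure, "including subjects that do not have the EMPOWER PG successfully implanted". Section 11.1.2.4 does the same to 365 days for Safety Endpoint 2. The SAP text supplied adds nothing on subject class or follow-up after a failed attempt.

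**The concern.** The minimum follow-up after a failed EMPOWER procedure exists to detect harm from that procedure; 9.2.2 gives this as its reason. The 9.2.3 clock starts at a different procedure. When the S-ICD came first, part or all of the 30 days can have elapsed before the EMPOWER attempt takes place.

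A failed attempt still involves femoral venous access and may involve catheter work in the right ventricle. Section 18.1 lists perforation with effusion or tamponade, arteriovenous fistula, pseudoaneurysm, thrombosis and infection among the risks. A subject withdrawn within days of the attempt stays in both safety endpoint sets but contributes little observed time, and a complication that appears after withdrawal is not recorded. Two sites could also handle identical subjects differently and both be following the protocol.

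**Working it through.** The check is date arithmetic plus a side-by-side reading. There is no sample size or power figure to reproduce.

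**Inputs**

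- 9.2.3: 30 days, counted from the S-ICD implant.
- 9.2.2 and 10.3.1.10 (first paragraph): 30 days, counted from the attempted implant.
- 10.3: EMPOWER first and S-ICD second is recommended, not required. The two procedures may fall on different days.
- Figure 7-1: the two implants lie within 30 days of each other when both devices are de novo.

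**Step 1: the two clocks.** Let k be the number of days from the S-ICD implant to the failed EMPOWER attempt, negative if EMPOWER was attempted first. Then the required follow-up after the attempt is

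- under 9.2.3: max(0, 30 - k) days;
- under 9.2.2 and 10.3.1.10 (first paragraph): 30 days for every k.

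| Sequence | k | 9.2.3 | 9.2.2 / 10.3.1.10 |
|---|---|---|---|
| EMPOWER attempt 30 days before S-ICD | -30 | 60 | 30 |
| EMPOWER attempt 10 days before S-ICD | -10 | 40 | 30 |
| Same day | 0 | 30 | 30 |
| S-ICD 10 days before attempt | 10 | 20 | 30 |
| S-ICD 20 days before attempt | 20 | 10 | 30 |
| S-ICD 29 days before attempt | 29 | 1 | 30 |
| S-ICD 30 days before attempt | 30 | 0 | 30 |
| Pre-existing S-ICD, e.g. 365 days | 365 | 0 | 30 |

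The clocks differ to the subject's disadvantage only when k > 0.

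**Step 2: which clock governs?**

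*S-ICD implanted in the study.* The second paragraph of 10.3.1.10 classes the subject as Partial Implant, which leads to 9.2.3. The description of Attempt in 9.5 agrees, because this subject did receive one device for the study. The and/or in the 9.2.2 definition nevertheless also covers the subject. The explicit routing gives the shorter clock, so the rows with k from 1 to 30 are a real shortfall.

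*S-ICD present before enrollment.* The wording of 9.2.3 fits: one device in place, EMPOWER introduced, full system not achieved. Its 30 days could have ended before enrollment. But 10.3.1.10 sends to Partial Implant only those whose S-ICD was implanted as part of the study, which leaves this subject under its first paragraph as Attempt. Sections 9.2.2 and 9.5 point the same way. The last row of the table is therefore a conflict between passages.

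**Step 3: is 9.2.3 out of line with the rest?** The other 30-day minimums run from the procedure being watched: attempted implant (9.2.2), unsuccessful EMPOWER implant (10.3.1.10), unsuccessful S-ICD implant (10.3.2.7) and explant (9.5, 10.12). Only 9.2.3 lets an earlier procedure start the clock for a later one.

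**The case against.** The strongest reply is that the protocol, read as a whole, already requires 30 days after the attempt. Section 9.2.2 literally includes these subjects and is mandatory, while 9.2.3 only permits withdrawal. In the recommended order, or on the same day, 9.2.3 itself gives 30 days or more. A shortfall needs the S-ICD first on an earlier day, and zero days needs the full spacing in Figure 7-1. Withdrawal is discouraged in 9.5, which also asks for open adverse events to be closed or documented as chronic. The tipping-point analyses in 11.1.1.3 and 11.1.2.4 include subjects without a successful implant.

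Much of this stands, and it limits the point. It does not remove it. If 9.2.2 applies, the same subject is under one rule that requires follow-up and another that releases earlier, and 10.3.1.10 directs the site to the second when the S-ICD was implanted in the study. The recommended order is only a recommendation. Closing open events does nothing for a complication that has not yet appeared, and a tipping-point analysis tests sensitivity to missing outcomes without recovering them.

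Two stronger readings are tempting. A reader might infer that anyone enrolled with an existing S-ICD can be released on the day of a failed attempt. Section 10.3.1.10 (first paragraph) and 9.2.2 say otherwise, so the documents support only a conflict. A reader might also infer that the Kaplan-Meier complication-free rate is biased upward. That would require withdrawn subjects to have a higher later risk than those who remain, and the documents give no figure for this. These subjects have no EMPOWER PG in place, and Attempt subjects are themselves withdrawn once their minimum of 30 days is met, so the difference between the rules concerns only the first 30 days after the attempt.

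**Conclusion.** The inconsistency is real and narrow. For an S-ICD implanted in the study k days before a failed EMPOWER attempt, the explicit routing gives a required follow-up after the attempt of max(0, 30 - k) days, against 30 days under the protocol's own Attempt rule. It reaches zero at k = 30. For a pre-existing S-ICD, the passages disagree. Same-day and EMPOWER-first subjects are unaffected.

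The size given is the shortfall in required days, not in observed days, since a site may follow a subject for longer. The documents give no count of failed attempts, of S-ICD-first sequences or of early withdrawals, so the number affected could be zero. The direction and size of any effect on Safety Endpoints 1 and 2 cannot be computed. A test against a performance goal can turn on one event, but that is true of any such test and does not measure what this rule might hide.

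The case for correction rests on complete observation of procedure-related harm in subjects whom the plan counts in its safety sets, and on having one rule that every site applies alike.

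**What to change.** Reconcile 9.2.2, 9.2.3 and 10.3.1.10 so that every subject with a failed EMPOWER attempt has one class and one clock.

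- In 9.2.3, count the minimum follow-up from the attempted EMPOWER procedure as well as from the S-ICD implant, with withdrawal possible only when both periods are complete. This carries over the existing 9.2.2 rule; it concerns study withdrawal and data collection, not treatment.
- State that this includes subjects enrolled with a pre-existing S-ICD.
- Remove the overlap between the 9.2.2 and 9.2.3 definitions, and align both paragraphs of 10.3.1.10 and the description of Attempt in 9.5. Either class will serve if the clock is the same.
- If any subject has already been withdrawn under 9.2.3, report the time from the EMPOWER attempt to last contact.

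The cost is one sentence plus aligned cross-references, and a phone contact, which 9.2.2 already accepts, for what should be a few subjects. Sample size, alpha and endpoint definitions do not change.

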## 9.2.4 Implant

**Implant** - refers to a subject who has been enrolled in the MODULAR ATP Clinical Study and is successfully implanted with the S-ICD **and** EMPOWER PG device per the study protocol (this includes those subjects previously implanted with an S-ICD System). Implant subjects are followed in accordance with the follow-up schedule included in this protocol and included in analyses of safety, effectiveness, and performance based on provisions discussed in **Section 11**.

## 9.3 Access to EMPOWER MPS Programmer Software and S-ICD System mCRM Programming

If a subject classified as either "Partial Implant" (those with the EMPOWER PG implanted, but not an S-ICD system) or "Implant" seeks routine or emergency care in a facility or from a physician who is not a study investigator, there may be a delay in:

- accessing the EMPOWER PG's data due to the need to secure access to the Programmer Software Application Model 3870, or
- accessing programmable mCRM parameters of the S-ICD device due to the need to provide a device-specific PIN, which is only available to trained study personnel with authorized access as part of the MODULAR ATP Clinical Study
  - Note: Non-investigational S-ICD parameters continue to be accessible at all times.

Trained study personnel (ie, BSC personnel or trained site personnel) are required to be present to access the Programmer Software Application Model 3870 and investigational features of the S-ICD (mCRM parameters) and report their use in these circumstances.

## 9.4 Strategies for Recruitment and Retention

The MODULAR ATP Clinical Study will include subjects deemed at risk for monomorphic ventricular tachycardia (MVT), SCD, and who are indicated for an ICD (Section 8.2). The incidence of SCD increases markedly with age regardless of sex or race: Accordingly, the SCD rate is estimated to range from 1.40 per 100,000 person-years in women to 6.68 per 100,000 person-years in men. SCD in younger individuals has an estimated incidence of 0.46–3.7 events per 100,000 person-years, corresponding to a rough estimate of 1100–9000 deaths in Europe and 800–6200 deaths in the USA every year. The inclusion and exclusion criteria are not expected to have a negative effect on recruitment or retention of said populations. In the United States, the subjects eligible for inclusion in this study are likely to be a mixture of private payer and Medicare patients due to their expected age and the results of this study are likely to be generalizable to a Medicare population.

## 9.5 Withdrawal

All subjects enrolled in the clinical study (including those withdrawn) shall be accounted for and documented. If a subject withdraws from the clinical study, the reason(s) shall be

Reasons for withdrawal include, but are not limited to:

- Subject who does not receive either device for the purpose of supporting the study (EMPOWER PG or S-ICD). This includes subjects classified as "Intent", and those classified as "Attempt", according to the definitions in **Section 9.2**.
- Subject found to be ineligible to participate in the study prior to implant of the S-ICD and/ or EMPOWER PG (refer to **Section 9.2** for further information on follow up requirements)
- Physician discretion
- Subject choice to withdraw consent
- Explant of the investigational device(s) (EMPOWER PG and/ or S-ICD converted with clinical firmware) \*; subjects should be followed at least 30 days (either in-clinic or phone contact) post-explant of the mCRM Coordinated System to assure there are no associated adverse events or to assure the resolution of any adverse events associated with the explanted mCRM Coordinated System.
  - **\*Note**: this provision includes explant of the EMPOWER PG in all subjects, and the S-ICD in the case where the device has had clinical firmware uploaded.
- Lost to follow-up
- Death

While study withdrawal is discouraged, subjects may withdraw from the MODULAR ATP Clinical Study at any time, with or without reason, and without prejudice to further treatment. In cases of study withdrawal where the EMPOWER PG remains actively implanted, the subject should be informed that he/she will need to continue to have the EMPOWER PG evaluated per BSC's recommended follow-up (1, 3, 6 months and every 6 months) at a MODULAR ATP Clinical Study site where there is access to the investigational software (Model 3870) to interrogate the EMPOWER PG.

All applicable case report forms up to the point of subject withdrawal and an End of Study Form must be completed in eDC.

Additional study data may no longer be collected after the point at which a subject has been withdrawn from the study or withdraws his/her consent, for whatever reason. All open adverse events should be closed or documented as chronic. Data collected up to the point of subject withdrawal may be used.

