### 10.12 Revisions, Replacements and Explants

If the S-ICD electrode, S-ICD PG, and/or EMPOWER PG are surgically revised, explanted, or removed from service after the initial implant procedure, or the S-ICD PG, EMPOWER PG is permanently programmed off, or disabled, the associated Device Tracking Form is used to record changes to the system, including rationale for the change.

Subjects with the EMPOWER PG or S-ICD with clinical firmware implanted will continue to be followed in the study. Subjects undergoing explant of the mCRM Coordinated System must be followed at least 30 days post-explant (either in-clinic or phone contact) to assure there are no associated adverse events, or to assure the resolution of any adverse events associated with the explant. These subjects must be withdrawn from the study after satisfying the follow-up period of at least 30 days; refer to **Section 9.5** for more information on study withdrawal.

If the EMPOWER PG is retrieved, procedure times of the device retrieval including fluoroscopy time, sheath in/out times, and retrieval catheter in/out times, as well as the outcome of the retrieval procedure will be collected. The explanted EMPOWER PG must be returned to BSC for returned product analysis. A copy of the Combined Follow-up Report from the programmer before the EMPOWER PG is taken out of service or explanted should be obtained. If the S-ICD with clinical firmware is explanted, it must be returned to BSC for returned product analysis. A copy of the S-ICD Summary Report before the S-ICD is taken out of service or explanted should be obtained. Table 10-18 lists the data required for system revisions.

Document any subsequent implant of another EMPOWER PG or S-ICD, regardless whether the previous EMPOWER PG is explanted or not, on the appropriate eCRF. These subjects should continue with the original follow-up schedule established using the initial Time 0.

Regardless of which device is revised or replaced, collect the following data.

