#### 11.1.3 Secondary Safety Endpoint: All-Cause Survival from Implant through 2 Years Post-Implant

The Secondary Safety Endpoint will be assessed for all implant subjects. Safety will be confirmed by evaluating the 2-Year all-cause survival rate post implant. Deaths due to any reason will count against this endpoint. Data from this endpoint will be used to evaluate the longer-term safety of the EMPOWER PG for the purposes of obtaining CMS approval and Medicare reimbursement. This analysis will be performed when all implanted subjects have been followed for a minimum of 730 days. In order to control the overall study Type I error rate, this endpoint will only be evaluated if Safety Endpoint 1,the primary effectiveness endpoints, and the Secondary Effectiveness endpoint are successful.

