#### 11.1.3.2 Sample Size

A sample size of 123 implanted subjects followed for 2 years is required to evaluate the Secondary Safety Endpoint. This sample size was calculated based on a one-sided normal approximation for a single binomial proportion, using SAS Version 9.4 with the following assumptions:

- Performance goal = 85%
- Significance level = 2.5% one-sided
- Power = 80%

Given an expected attrition rate of 40%, 275 subjects are needed, which is less than the 300 enrolled subjects. This means that the overall study sample size is not being driven by this endpoint.

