#### 11.1.3.3 Statistical Methods

Endpoint analysis will be performed on all implanted subjects.

The survival rate from the implant through 730 days post-implant will be calculated using Kaplan-Meier methodology. Deaths for any reason will count as an event for this endpoint. The 5% one-sided lower pointwise confidence limit of the survival rate will be calculated via log-log methodology and compared to the performance goal of 85%. If the lower confidence limit exceeds 85%, the null hypothesis will be rejected.

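### The 2-year survival endpoint has no provision for vital status after withdrawal and no missing-data sensitivity analysis, and Sections 9.5 and 10.12 differ on single-device explant

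*Protocol*

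**What the plan says.** **Data after withdrawal.** Protocol Section 9.5: "Additional study data may no longer be collected after the point at which a subject has been withdrawn from the study". The sentence goes on to include withdrawal of consent and applies whatever the reason. The listed reasons include physician discretion, explant and loss to follow-up. Nothing is said about vital status.

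**The endpoint.** Section 11.1.3: "Deaths due to any reason will count against this endpoint". Section 11.1.3.3: "The survival rate from the implant through 730 days post-implant will be calculated using Kaplan-Meier methodology". The analysis set is all implanted subjects, the goal is 85%, and the result is intended for CMS approval and Medicare reimbursement. Section 11.1.3.2: "Given an expected attrition rate of 40%, 275 subjects are needed". Neither Sections 11.1.3 to 11.1.3.3 nor the SAP text names a missing-data analysis for this endpoint.

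**The other endpoints.** Sections 11.1.1.3, 11.1.2.4, 11.1.4.3 and 11.1.5.3 each plan a tipping point analysis.

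**Explant.** Section 9.5 lists among the reasons for withdrawal "Explant of the investigational device(s) (EMPOWER PG and/ or S-ICD converted with clinical firmware", and its note adds that "this provision includes explant of the EMPOWER PG in all subjects". Section 10.12 says "Subjects with the EMPOWER PG or S-ICD with clinical firmware implanted will continue to be followed in the study". Of subjects whose Coordinated System is explanted, it says "These subjects must be withdrawn from the study after satisfying the follow-up period of at least 30 days".

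**The concern.** Kaplan-Meier is unbiased only if those censored have the same later mortality as those who stay. That is doubtful for subjects who leave after an explant, at a physician's discretion, or by losing contact. Death is also the outcome most easily ascertained without contacting the subject, yet Section 9.5 provides no route to it for people who have not refused.

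The protocol recognises the problem elsewhere. For both primary safety endpoints it pairs Kaplan-Meier with a tipping point analysis because of missing data, at 25% and 30% assumed attrition. The survival endpoint uses the same estimator over a longer period with 40% stated attrition, and has no such check. At stake is whether the survival figure offered for coverage can be read at face value.

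**Working it through.** **1. The plan's own figure.** 123 / (1 − 0.40) = 205, not 275. The stated 275 would need 275 × 0.60 = 165 evaluable subjects, or attrition of 1 − 123/275 = 55%. So 123, 40% and 275 cannot all be right, and 40% is a weak guide to the amount of censoring. The size calculation below therefore uses 10–35%.

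**2. The explant sections side by side.**

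| Situation | Section 9.5 | Section 10.12 |
|---|---|---|
| Both devices explanted | Listed reason for withdrawal; at least 30 days' follow-up | Withdrawal required after at least 30 days |
| EMPOWER PG only explanted | Listed reason, in all subjects | Followed if the converted S-ICD remains |
| Converted S-ICD only explanted | Listed reason | Followed if the EMPOWER PG remains |

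The sections agree on the first row. On the other two, a subject could be censored under one section and followed to day 730 under the other.

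**3. Size of the bias.** All inputs here except the 85% goal and the 730-day horizon are assumptions. Let h be the yearly death hazard on study, c the withdrawal hazard, kh the death hazard after withdrawal, and T = 2 years.

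- Withdrawal share (ignoring death): w = 1 − exp(−cT)
- True survival: S = exp(−(c+h)T) + ∫₀ᵀ c·exp(−(c+h)t)·exp(−kh(T−t)) dt
- What Kaplan-Meier estimates: exp(−hT)

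Set S = 0.85, so the null hypothesis is true, and solve for h. Example with w = 25%, k = 2: c = −ln(0.75)/2 = 0.1438. Solving gives h = 0.0722, and Kaplan-Meier targets exp(−0.1444) = 86.6%, an overstatement of 1.6 points.

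The table gives the overstatement in points, then the share of simulated trials whose log-log 97.5% lower limit exceeds 85% (N = 250, 20,000 runs per cell).

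| Withdrawn | k = 1.5 | k = 2 | k = 3 |
|---|---|---|---|
| 10% | 0.3; 3% | 0.6; 4% | 1.2; 6% |
| 15% | 0.5; 3% | 1.0; 5% | 1.7; 9% |
| 25% | 0.8; 4% | 1.6; 7% | 2.8; 17% |
| 35% | 1.2; 5% | 2.2; 10% | 3.7; 27% |

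With k = 1, or with full vital status, the pass rate is about 2%. Repeat simulations of this design span about 2% to 29% over the grid. The 97.5% limit matches the 2.5% level in Section 11.1.3.2. Section 11.1.3.3 instead words the limit as 5%, a separate inconsistency. At a 5% level, with 25–35% withdrawn, the false-pass rates become 15–19% (k = 2) and 28–42% (k = 3).

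**4. If survival is well above the goal.** The expected survival is not given in the text. Solving the one-sample formula n = [(1.96√(p₀q₀) + 0.84√(p₁q₁)) / (p₁ − p₀)]² = 123 with p₀ = 0.85 gives p₁ of about 93.2% (91.9–94.0% under other variance choices). Under the same model with 40% actually withdrawn:

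| Kaplan-Meier reads | True, k = 2 | True, k = 3 | True, k = 5 |
|---|---|---|---|
| 93% | 91.5% | 90.1% | 87.5% |
| 90% | 87.9% | 86.0% | 82.5% |

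**5. What a tipping point analysis would show (illustrative counts, exact 2.5% test against 85%).**

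- 205 implanted, 9 deaths among 123 known (7.3%), 82 unknown: at most 20 deaths are allowed in total. The conclusion reverses at 21 − 9 = 12 deaths among the unknown, or 12/82 = 14.6%, twice the known rate.
- 300 implanted, 13 deaths among 180 known (7.2%), 120 unknown: at most 32 are allowed. It reverses at 33 − 13 = 20, or 20/120 = 16.7%, 2.3 times the known rate.

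**The case against.** The case against is substantial on scope and size.

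- *A reader might infer that the trial has no missing-data analysis.* It does, for four endpoints. The gap is confined to this one.
- *A reader might infer that all follow-up stops at withdrawal.* Subjects whose Coordinated System is explanted are followed at least 30 days first, and three documented contact attempts precede closure as lost. Clinical checks of an active EMPOWER PG are still advised, though they yield no study data. Stopping collection when consent is withdrawn is expected. What remains is the absence of any vital-status provision for the other reasons.
- *A reader might infer that Section 9.5 requires withdrawal after any explant.* It lists possible reasons. The mandatory wording is in Section 10.12 and concerns the Coordinated System. The note about EMPOWER PG explant in all subjects still conflicts with continued follow-up, but it affects only single-device explants, whose frequency is not given, and it does not drive the figures above.
- *A reader might take 40% as the share of analysed subjects censored.* Its base is not stated. The 25% in Section 11.1.1.2 is of enrolled subjects, and enrolment is at consent. If the 40% is built the same way, it includes subjects never implanted, who are outside this endpoint. It may also include deaths, since death is a listed reason for withdrawal.
- *The endpoint is secondary and last in the testing order* (Section 11.5.1), so study success does not depend on it. That stands and limits the weight of the point. The endpoint still has its own stated use in reimbursement.
- *Consent pages are not in the public text.* Consent may already permit a records check. Section 9.5 as worded would still bar using it for study data.

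**Conclusion.** The point holds for the Secondary Safety Endpoint only. The plan has no vital-status provision after withdrawal other than by refusal, no sensitivity analysis for missing survival status, and two sections that differ on single-device explant.

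The direction of bias is upward if those who leave have higher mortality; its size is unknown. The ranges in the working rest on assumed withdrawal shares, constant hazards, and a raised hazard for every withdrawn subject, including those leaving for reasons unrelated to health. They run from negligible to material. The documents do not support saying that the endpoint will pass falsely. If Kaplan-Meier survival comes out near 93%, even a five-fold hazard after 40% withdrawal leaves true survival above 85% in this model. The conclusion is exposed mainly when survival is closer to the goal. This is worth correcting, but it does not threaten the primary conclusions.

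**What to change.** 1. **Section 11.1.3.3:** add a tipping point analysis like those for the other endpoints. Report how many deaths among implanted subjects of unknown day-730 status would reverse the conclusion, and compare that death rate with the rate in followed subjects. Without the comparison the result says little: in the illustrations above, counting every unknown subject as dead gives about 55–57% survival, so a tipping point will almost always exist. Cost: wording only.
2. **Section 9.5:** allow vital status at day 730 to be obtained from medical or public records for withdrawn or lost implanted subjects, where consent and local law allow and the subject has not refused. Cost: possibly a consent sentence, which would reach only new or reconsented subjects, and a one-time records check.
3. **Sections 9.5 and 10.12:** reconcile them on study follow-up after explant of one device, so that sites apply the same rule. Which rule is adopted is for the sponsor and investigators. Cost: wording only.
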